## Human Subjects

### 1. RISKS TO THE SUBJECTS

#### a. Human Subjects Involvement and Characteristics.

##### i. Inclusion Criteria.

Subjects will be 280 men and women, age 18 and older, who meet DSM-5 criteria for cocaine use disorder and who are beginning intensive outpatient treatment at a community-based substance abuse treatment clinic. All subjects must be willing to sign informed consent and must be able to pass (6 or more correct responses) a brief, 8-item quiz inquiring about study procedures, such as “Do you get to choose which treatment group you go into?” and “Can you drop out of the study at any time and still come to regular treatment at this clinic?” In our past studies, only rarely have potential subjects failed to pass this quiz, which ensures understanding of study procedures.

Participants with substance use disorders in addition to cocaine may participate in this trial to enhance generalization of findings; the vast majority of patients with cocaine use disorders have more than one substance use diagnosis. These clinics do not offer outpatient treatment services to patients experiencing physiological withdrawal symptoms, and such patients will have been referred to, and completed, an alcohol detoxification prior to initiating the intensive outpatient treatment program from which this study will recruit.

##### ii. Exclusion Criteria.

Exclusion criteria are serious uncontrolled psychiatric illness (acute bipolar disorder, schizophrenia, or suicidal behavior); in recovery from pathological gambling or current pathological gambling diagnosis and desiring to stop or reduce gambling (because of potential concerns of similarity of prize reinforcers and gambling even though no increases in gambling have been reported; Petry & Alessi, 2010; Petry, Kolander et al., 2006); and do not speak English (all treatment is provided in English at these clinics so we expect no patients who present to these clinics to be disqualified based on the language criteria; local clinics provide substance abuse treatment services in other languages).

Participants in the main trial will be invited to participate in the fMRI sub-study associated with this project following randomization to Groups A or C. Only patients assigned to these two groups will be offered participation in the fMRI sub-study to conserve costs associated with fMRI; these two groups are expected to show the greatest differences with respect to treatment outcomes and hence are also expected to show the greatest pre to post differences with respect to neural changes during treatment. Participants interested in the fMRI sub-study will be screened and excluded from the fMRI sub-study for current use of any medication that affects blood flow (e.g., for hypertension) and for any conditions that are contra-indicated for fMRI scanning: claustrophobia, presence of ferromagnetic metallic implants, prior severe head trauma, color blindness, left handedness, and pregnancy (assessed via urinalysis on day of scanning).

##### iii. Ineligible Patients.

Some patients will choose not to enroll or will not qualify for the main study. These patients may continue receiving standard services at the clinic in which they are enrolled, and they may also be referred to their treatment provider or other facilities (e.g., other substance abuse treatment clinics, mental health treatment facilities, or to a gambling treatment clinic such as Problem Gambling Services in CT) as appropriate.

Similarly, some participants in the main trial will be ineligible for or not want to participate in the fMRI sub-study. Prospective participants will be informed that declining the invitation to participate in the neuroimaging component will not affect their ability to participate in the main trial or their ability to receive treatment at the clinic or elsewhere.

iv. Treatment Clinics, Services, and Patient Population.

Patients will be recruited from Alcohol & Drug Recovery Centers (Hartford, CT), Hospital of Central CT and Farrell Center (both New Britain, CT), Carlson Recovery Centers (Springfield, MA), Regional Network of Programs (Bridgeport, CT), and The Village (Hartford, CT). These centers all provide comprehensive substance abuse treatment services, including an intensive day program and long-term aftercare. The clinics were selected because they have similar treatment approaches, provide equal intensities of care, and treat analogous patient populations.

At each clinic, about 8-12 patients enter the intensive day program each month from which subjects for this study will be recruited. Intensive outpatient care (up to about 6 hours/day, 3-5 days/week) is provided for 3-4 weeks (depending on need), and then partial care (2-6 hours/day, 2-3 days/week) for another 2-4 weeks. Level of care is gradually reduced to 1-2 group/week during aftercare. Aftercare is recommended for 12 months, although very few patients continue attending treatment for this duration of time. About 40-60% of patients entering each clinic have a cocaine use disorder; the remainder have primarily an alcohol or marijuana use disorder. For over 15 years, we have been conducting similar studies at these and other community based clinics and the clinics have never encountered a problem meeting recruitment goals or integrating studies in the context of standard care; non-study patients are intermixed with study patients within the same group sessions without problems because the reinforcement intervention and study procedures are implemented on an individual basis, and at least half the patients in treatment at the clinics are not involved with the study.

- b. Sources of Materials. Research material includes interviews, questionnaires, audiorecordings of interviews and sessions, abstraction of attendance data from clinical charts, and observation of patients by study staff. Breath samples and urine samples will be tested for evidence of alcohol and illicit drugs, e.g., stimulants (cocaine, amphetamine and methamphetamine), opioids, benzodiazepine and THC. None of these materials will be available to legal, educational, or employer representatives. Data obtained for research purposes will be at no cost to patients. Urine and breath samples obtained for study purposes will not be shared with clinical staff except in the case of an emergency (patient deemed a threat to himself or others). Electronic data are stored on password-protected secured computers in locked facilities.

Sources of material for the fMRI portion (for those eligible) will include performance measures on the tasks (e.g., Stroop, MID), and the MRI data collected. The performance measures will be collected via computer as will the MRI data during scanning on a 3T magnet. Electronic data are stored on password-protected secured computers in locked facilities.

- c. Potential Risks. Risks associated with participation in this research study include the following:
- i. Disappointment if participants are not assigned to their preferred treatment group;
  - ii. Discomfort from being asked questions about alcohol and drug use, medical problems and histories, HIV risk behaviors, psychosocial problems, and submitting breath and urine samples;
  - iii. Difficulties that may arise from discontinuation of study cellular phone service if patients fail to submit requested urine samples.
  - iv. Potential breach of confidentiality.
  - v. Risks associated with participating in the fMRI sub-study are considered minor as it is a non-invasive procedure and does not involve any radiation, but include the hazard from loose metal objects and feelings of claustrophobia associated with all MR imaging of the head.

2. ADEQUACY OF PROTECTION AGAINST RISKS

a. Recruitment and Informed Consent.

Study patients will be recruited from individuals initiating treatment at one of the participating centers. All potential clients will receive an explanation of the study protocol, its potential risks and benefits, and alternative treatment available. Following resolution of any questions, patients who pass a brief quiz regarding the nature of the study and consent to participate will be asked to sign the study consent form and HIPAA document. A signed copy of the consent and HIPAA forms will be given to each patient. As noted above, patients who choose not to participate in the study or who are deemed ineligible for it will receive standard services at the center and may also be referred elsewhere for services if indicated.

An opt-in statement regarding audiorecording in the consent form will be utilized for recording of the interactions between research assistants and study participants, including baseline and follow-up interviews. These audiorecordings are utilized only for quality insurance procedures, to rate research assistants according to set standards in interview and treatment administration. Patients may participate in the study even if they do not choose to allow audiorecording of the interviews (in our prior studies, less than 10% of patients refuse audiorecording). The audiorecording consent form will explain that the purpose is to rate the research assistants' interviewing skills.

Recruitment for the fMRI sub-study will be separate from the main study, utilizing a unique informed consent form as relates to this sub-study. After completing the baseline assessment and being randomized as part of the main study, those who are assigned to Groups A and C, and who appear to possibly be eligible for fMRI will be screened for the fMRI sub-study, and additional fMRI exclusionary criteria assessed. Those who do not meet fMRI exclusionary criteria, and who choose to participate in the fMRI sub-study after receiving full informed consent for the fMRI study, will then be scheduled for fMRI. Patients may choose not to participate in the fMRI sub-study and still continue in the main study, as well as receive standard care at the clinic. Decisions whether or not to do the fMRI study will have no bearing on the primary study, or non-study, procedures.

b. Protection Against Risks. The following will protect against potential risks:

- i. Random group assignment is used so that patients have about a 78% chance (220 of 280) of being assigned to a reinforcement group (60 of 280 are in the standard care condition; see power analyses), and patients may voluntarily end study participation if they are dissatisfied with their assignment.
- ii. The interviews and sample collections are brief, patients may skip questions or take a break if uncomfortable, and the particular sample assays chosen are intended to minimize discomfort. All participants will be informed (in the informed consent form and at each visit) that in weeks 1-3, they will be expected to submit urine samples twice weekly, according to their own pre-set schedule at the beginning and end of each week (M-Th, M-F, or T-Th). To maintain cellular phone service, they cannot miss more than one requested sample in a 7-day period. Participants will be informed that in weeks 4-24, they will be phoned or texted (their preference) each morning of their twice weekly possible testing days and told whether they need to submit a sample that day. If they fail to submit a requested sample, they will be phoned and/or texted later that same afternoon and told that they MUST submit a sample when requested at the next testing day to maintain cellular service. The consent form will state explicitly that all study participants will be asked to submit between 15 and 35 samples in weeks 4-24 to maintain cellular service, that failing to provide a sample when requested will result in the need to provide samples

on the next two consecutive testing days, and that missing two requested samples in a row will result in a discontinuation of cellular service.

- iii. Participants will be informed of how to reinstate cellular service in the consent form and after any missed sample (i.e., if they submit a sample, discontinued service will be reinstated within about 24 hours). Additionally, if cellular service is discontinued, they will be contacted, informing them of the process about how to restore cellular phone service (i.e., submit a sample). If patients are uncomfortable returning to the treatment clinics to submit samples, they can also submit samples at UCHC, which is on the bus lines from Hartford and New Britain. Patients will be also informed in the consent form that if they wish to alter testing days they can do so at any time with one week's notice.
- iv. All data will be coded by number, not name, and a "key" form will be kept in a separate locked file cabinet. No information will be provided about the patients enrolled in this study to anyone outside of the clinical and research teams, except in emergency situations (e.g., severe intoxication, participant deemed a threat to him/herself or others) or as required by law. Locators (identified by patients to assist in finding them if needed for follow-ups) will not be given any information regarding the participant's treatment status, only that we are trying to reach them regarding their participation in a health study.

Digital audio recordings of interviews and sessions will be stored as .wma files. All recordings will be labeled by number, not name, and the "key" form will be kept separate in a locked file cabinet. These files will be transferred from the digital recorder to a secured folder on the UCHC network drive after the recording is completed. This folder will only be accessible to research staff. Once files are transferred to the secure folder, they will be deleted from the recorder itself. When not in use, recorders will be stored in locked cabinets with data. Subjects will not be identified by name on recordings. Only study personnel will review the recordings for training, supervision, and adherence monitoring purposes. We will obtain consent to audiorecord, and patients may participate in the study without allowing audiorecording. The .wma files will be permanently deleted at the end of the study.

Any study participant who arrives at the clinics grossly intoxicated is not provided any clinic services that day. This project will strictly adhere to these clinic rules, and patients who appear to be intoxicated or smell strongly of alcohol will not be allowed to participate in group or individual therapy, or complete follow-up evaluations. Such patients will be immediately referred to clinic staff (e.g., clinic director) and/or asked to leave the center. If the patient is deemed a threat to him/herself or others, police or emergency personnel will be contact to assist in the situation as required by law. Almost none of the patients who attend these centers have automobiles, but any patient who may have driven to the center will be requested to provide their keys to clinic personnel. If they refuse, police or emergency services may be contacted, as required by law.

- v. To protect participants who are eligible and agree to participate in the fMRI portion of the trial, all participants will be screened for appropriateness for fMRI using a screening form. All participants will be screened using a screening form for any metallic objects that they may be holding or have implanted in their bodies and all potential participants with metallic implants will be excluded. Individuals with occupational histories that might pose problems for MRI will be required to undergo additional safety procedures (e.g., individuals who have performed welding without eye protection will be required to obtain orbital x-rays prior to scanning). Similarly, other potential sources of metal (e.g., tattoos that contain magnetically sensitive metals), along with pregnancy will be investigated for compatibility with MRI. The Screener will be repeated prior to imaging to ensure that

participants are not bringing any metallic materials into close proximity of the magnet, where they might be pulled toward the magnet or heated by the magnet. As a routine part of neuroimaging, individuals are also required to walk through a metal detector prior to entering the room with the scanner.

Further, on the day of scanning, information about menstrual cycle (for women), tobacco use (for smokers, including pre- and post-scan carbon monoxide (CO) assessments), alcohol use (pre- and post-scan breathalyzer measures) and substance use (urine toxicology and self-report) will be obtained. Participants who are smokers will be given the opportunity to smoke about one hour prior to scanning in order to avoid acute intoxication or withdrawal effects from tobacco. Consistent with our prior fMRI studies, participants who are experiencing acute drug intoxication or withdrawal will not be scanned. Similarly to data from the main trial, all fMRI data will be coded by a unique code, and not names. Electronic data are stored on password-protected secured computers and paper information with PHI linked to the computerized data is kept secured in locked file cabinets in locked facilities

- c. Potential Benefits of the Proposed Research to the Subjects and Others. The anticipated benefits to patients in the study include careful evaluation of their medical and psychiatric status, drug and alcohol use, and a potential for reducing their cocaine use. Patients in all groups will receive \$35 in gift cards for the baseline assessment, and \$50 for all others, plus \$25 in gift cards for computer/impulsivity assessments (as well as the chance to win an additional \$5 based on task responses). Patients will receive \$25 for returning the cell phone in working condition. They will receive a study-paid cell phone (or \$25 per month in the form of gift cards to be given at the 3 and 6 month assessments, if they choose to use their own phone, for a total of \$150) so long as they provide study-requested samples, estimated average of 18-23 per patient. Depending on group assignment, patients may also receive prizes for submitting stimulant negative samples. Payment for participation in the fMRI sub-study is \$100 per completed session, pro-rated to \$20 per hour for incompleting sessions, to a maximum of \$200 in total for two completed sessions.

Benefits to society include a potential improvement in the effectiveness of treatment for patients with substance use disorders.

- d. Importance of the Knowledge to be Gained. The potential risks of these treatments are minor compared to the risk incurred by patients with cocaine use disorder. The risk/benefit ratio appears favorable.
- e. Women/Minorities/Children. We expect the gender and racial composition to reflect the demographics of the clinic members. About 50% of patients at each clinic are female, and >45% are members of ethnic minorities (30% African American and 15% Hispanic, all of whom are fluent in English as treatment is only provided in English at these clinics, and 2% Native American, Asian American, or other). These proportions allow for exploratory analyses of gender and racial/ethnicity effects, as we have done previously (e.g., Montgomery et al., 2012).

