**A. Standard treatment (weeks 1-24):** Patients assigned to this condition will receive standard care, consisting of group therapy, including daily planning, 12-Step therapy, relapse prevention, coping and life skills training, recreation training, focus groups for depression and anxiety, and AIDS education. Intensity starts at 3-4 groups

per day 3-5 days per week and is gradually reduced to 1 aftercare group per week. Individual and family counseling is provided on an as-needed basis, usually only for crises. Groups are led by recovering individuals, nurses, and MA level counselors. Format and intensity of care is similar across clinics.

Study patients will undergo regular urine and breath sample monitoring for 24 weeks. In the first three weeks, twice weekly testing will be arranged, coinciding with early and late weekdays of clinic attendance (M-Th, M-F, Tu-Fri). Thereafter, days selected for sample collection will be randomly selected from patients' twice weekly preferred schedule (M-Th, M-F, or T-F), which may or may not coincide with group therapy, as some patients will have ceased attending groups. RAs will phone or text (patient's preference) on the morning of each testing day to inform them whether or not to leave a sample that day. For example, in weeks 4-9, a patient with a M-F schedule may be asked to come in on Mon, Mon, Fri, Mon, Fri, Mon in the respective weeks. Patients will be told to plan to leave a sample on each of their test days, and will be phoned or texted on average every other possible test day in weeks 4-9 and told they need not leave a sample that day. In weeks 10-24, days for sample collection will reduce to once every 2-3 weeks on average. Patients need only avail themselves for sample collection on two days per week (beginning and end of each week), and the schedule of availability can change over the 24-week period (e.g., from M-Th to T-F) so long as patients give at least one week notice. Patients will receive \$2 per requested sample submitted, plus a \$20 bonus if they submit all requested samples in a four week period (regardless of results). In the case of an excused absence, patients can come in the next day to submit a sample and still be eligible for the \$20 bonus.

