To ensure contact and submission of samples on requested days, patients will receive a study cell phone (allowing unlimited calls and texting) as long as they do not miss more than one requested sample in a row. If a patient fails to submit a sample on a testing day, the RA will phone the patient that afternoon/evening and remind him/her that if s/he fails to provide a sample the *next* selected testing day, the phone will be turned off. After a missed sample, the next two test days will be prompted for sample submission. For example, if a patient failed to submit a sample when requested on a Mon, that patient would be prompted for another sample that Thur, and the following Mon. If the patient missed the Thur sample (or any two prompted samples in a row), cell service would be discontinued. The goal is to obtain on average  $\geq 18$  samples from patients across 24 weeks and equivalent samples relative to Group C, so that objective indices of drug use will be available similarly across conditions. (To accommodate for the potential of higher test days that may occur in Group C patients who relapse, additional test days will be randomly selected based on running averages of samples obtained from patients in the adaptive condition; [name] has developed and maintained programs to automate sample selection days in ongoing and pilot trials). This system encourages submission of samples to accurately and consistently gauge drug use, without being unduly burdensome.

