Patients in this condition, as in Group A, will receive a study cell phone (or \$25/month toward their own cell phone service) if they maintain contact with research staff and submit samples when requested to do so. Because the reinforcement schedule for abstinence is set at twice weekly for 24 weeks, there is little reason to inform patients of reinforcement days throughout the study period. However, RAs will phone or text patients at the same frequency in this condition as in Groups A and C to inform them when "a sample is due to maintain cell phone service." If they fail to submit a sample when prompted, additional samples will be requested within the next week, as described in Group A. If two requested samples in a row are missed, then cell service will be discontinued. Reinstatement of cell service will be as described above.

In this manner, reinforcement for submission of negative samples is similar to that provided in traditional reinforcement interventions (pre-determined frequent urine testing). At the same time, prompting of urine sample submission (along with cell phone service for complying with submission) will be similar to other groups so that overall the same minimum number of samples should be obtained across conditions. In this manner, objective indicators of relapse to drug use will be obtained similarly across groups (see also Analyses).

Patients in this group can earn draws for providing negative samples in response to a cell phone prompt, and they may not have submitted these samples had they discontinued care in a traditional reinforcement intervention. In this sense, Group B is somewhat enhanced relative to traditional reinforcer interventions, and allows for a conservative test of Aim 2. Nevertheless, maximum draws per sample is only 1 when patients fail to submit negative samples twice weekly in this condition. Thus, the additional reinforcement for submission of samples by integrating cell phone prompted samples appears modest and unlikely to impact outcomes.

**C. Standard care + progressive VI reinforcement.** These patients receive standard care and earn draws with chances of winning prizes for submitting negative urine samples. However, relative to Group B, the frequency with which they are expected to submit samples to earn abstinence reinforcement decreases over time so long as they maintain abstinence. In the first phase, twice weekly samples are expected just like the other groups,

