with sample collection days occurring at the beginning and end of the week and coinciding with regular clinic attendance (when applicable) and patient preference for days (M-Th, M-F, or T-F). Once patients in this group achieve ~3 weeks of continuous abstinence, they will be expected to submit samples on average once a week for the next 6 weeks (phase 2). After 9 full weeks of abstinence, sample collection will decrease to every other week on average for the next six weeks (phase 3), and finally patients who maintain abstinence will be transitioned to a testing and reinforcement schedule of every three weeks on average for the final 9 weeks of the 24-week treatment period (phase 4). In total, an average of  $\geq 18$  samples will be scheduled over 24 weeks in patients maintaining abstinence. As in Groups A and B, patients will receive \$2 per requested sample submitted, plus a \$20 bonus if they submit all requested samples in a four week period (regardless of results). In the case of an excused absence, patients can come in the next day to submit a sample and still be eligible for the \$20 bonus.

As in Group B, patients earn 1 draw per negative sample, and draws earned increase by one draw for consecutive negative samples during the twice-weekly testing phase (phase 1). To accommodate for the reduced overall number of samples submitted relative to Group B and to maintain overall equal maximum reinforcement between conditions, once a patient moves to the phase 2 sample schedule (once a week) draws per negative sample increase by 2 draws for each consecutive negative sample provided. Draws continue to increase by 2 up to a cap of 25 draws per negative sample, which would be achieved after about 15 weeks of abstinence.

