If a patient fails to provide a sample or submits a positive sample, draws earned for the next negative sample reset to one, and then increase by one per consecutive negative sample. The frequency of testing and reinforcement also increases after a reset to rapidly reinstate abstinence. After a missed or positive sample, the patient will be asked to submit samples on all scheduled testing days for 2 consecutive testing days, earning 1 and then 2 draws if negative. Then, sample collection will resume to weekly on average for about another 2-3 weeks (earning 3, 4 and 5 draws if negative). Upon achieving 5 draws (~4 weeks of abstinence), number of draws earned will reinstate back to the highest level previously attained for the next negative sample, and sample collection frequency will coincide with whatever level the patient was previously at. In other words, a patient who had previously achieved 13 weeks of abstinence and was at every other week random testing would resume 21 draws per negative sample and every other week random testing once he has attained a month of abstinence following a lapse or missed sample. Using this schedule, patients who test negative on all test days will earn about 231 draws over the 24-week period, similar to Group B. As in other conditions, RAs will congratulate patients for each substance for which they test negative, and encourage them to discuss any use in group.

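### The 15 to 35 sample requests that all participants are to be told to expect in weeks 4-24 do not fit the plan's own testing schedule at either end

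*Combined protocol and SAP*

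**What the plan says.** In Human Subjects, section 2 (Adequacy of Protection Against Risks), item b.ii, the protocol commits the consent form to telling participants that "all study participants will be asked to submit between 15 and 35 samples in weeks 4-24 to maintain cellular service". It is worded as a range for everyone, not as an average or an example.

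The schedule behind it is in the Methods. All groups are tested twice weekly in weeks 1-3. For Group C: "Once patients in this group achieve ~3 weeks of continuous abstinence, they will be expected to submit samples on average once a week". That rate lasts six weeks (phase 2). Testing then falls to every other week on average for six weeks (phase 3) and to every three weeks on average for the last nine (phase 4). The Group C section puts the total at 18 or more samples on average over 24 weeks for patients who stay abstinent, and adds that "patients who test negative on all test days will earn about 231 draws over the 24-week period, similar to Group B". A positive or missed sample returns a Group C patient to more frequent testing.

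For Group A the rule is: "After a missed sample, the next two test days will be prompted for sample submission". For Group B: "If they fail to submit a sample when prompted, additional samples will be requested within the next week, as described in Group A". Phone service stops only after two requested samples in a row are missed. It does not depend on test results (Innovation, item 3).

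**The concern.** The range goes to participants, is tied to keeping their phone service, and sits under the heading on protection against risks. Discontinued phone service is itself one of the listed risks. A range given for all participants should contain what the schedule will ask of them. If it does not, some patients are told to expect more visits than they will have. Others, most likely those still using cocaine or missing samples, could be asked for more than the maximum they were told. The stake is the accuracy of the consent information, not the validity of the trial's comparisons.

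**Working it through.** **Inputs.** Two possible test days a week (Methods, Group A section). Weeks 4-24 are 21 weeks. Group C phase lengths and average rates are as given in the Group C section.

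**1. Reproduce the plan's totals for a Group C patient negative at every test.**

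- Phase 1: 3 weeks x 2 = 6
- Phase 2: 6 weeks x 1 = 6
- Phase 3: 6 weeks x 1/2 = 3
- Phase 4: 9 weeks x 1/3 = 3
- Total: 18, the plan's figure.

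Draws on those 18 samples: 1 to 6 in phase 1 (sum 21); 7, 9, 11, 13, 15, 17 in phase 2 (sum 72); 19, 21, 23 in phase 3 (sum 63); 25 three times in phase 4 (sum 75). 21 + 72 + 63 + 75 = 231, the plan's figure. The plan's own example, 21 draws for a patient with 13 weeks of abstinence on every-other-week testing, falls at the right place in this sequence.

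**2. Lower end.** Weeks 4-24 hold 18 - 6 = 12 requests on average, 3 below the stated minimum of 15. The plan's wording of 18 or more does not close the gap. Fifteen in weeks 4-24 means at least 21 in total, and three more samples at the 25-draw cap give 231 + 75 = 306 draws.

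Twelve is an average, so some of these patients will be asked 15 times or more. The plan does not give the mechanism for drawing test days, so I assumed three:

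| Assumed mechanism | Always-negative Group C patients with fewer than 15 requests |
|---|---|
| Each test day drawn independently at the phase's rate | 82% |
| Exactly one a week in phase 2, other days independent | 87% |
| Drawn by week (one a week in phase 2; each week at 1/2 in phase 3 and 1/3 in phase 4) | 91% |

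**3. How quickly the lower gap closes.** For a Group C patient who leaves phase 1 at the end of week w and is negative afterwards, requests in weeks 4-24 = 2(w - 3) + phase 2 to 4 requests in the weeks left:

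- w = 3: 0 + 6 + 3 + 9/3 = 12
- w = 4: 2 + 6 + 3 + 8/3 = 13.7
- w = 5: 4 + 6 + 3 + 7/3 = 15.3

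A single later lapse does much the same. The recovery sequence is two consecutive test days and then about three weekly samples, about 5 requests over about 4 weeks. In phase 3 this replaces 2 requests (12 - 2 + 5 = 15). In phase 4 it replaces 4/3 (12 - 1.3 + 5 = 15.7).

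**4. Upper end, Group C.** A patient who submits every sample but never reaches about 3 weeks of abstinence stays on twice-weekly testing: 21 x 2 = 42 requests, 7 above 35 (7/35 = 20%). By the formula in step 3, w = 17 gives 28 + 6 + 0.5 = 34.5 and w = 18 gives 30 + 6 = 36. Without a later lapse, 35 is passed only if phase 1 lasts through week 18 or beyond.

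**5. Upper end, Groups A and B.** A patient who misses the last test day of week 3 is prompted on the next two test days. If that patient submits on the first and misses the second, two more days are prompted, and so on. Missing every second prompt in this way gives prompts on 42 of 42 test days with never two misses in a row, so service continues.

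**The case against.** The strongest case against is about weight. The figure of 12 needs a patient with no positive and no missed sample for 24 weeks. Step 3 shows that a two-week delay in leaving phase 1, or one lapse in phase 3 or 4, already brings the count to about 15. For the patients affected, the stated range overstates the burden, which does them no harm. At the top, 42 is printed nowhere in the plan. In Groups A and B it takes a very particular pattern of misses, and in Group C it takes near-complete submission without about 3 weeks of abstinence up to week 18 or later. Participants are also told, alongside the range, that they will be contacted on both test days every week, that a miss adds the next two test days, and that submitting a sample restores service within about 24 hours. All of this stands, and it is why the point is minor. It does not make a range stated for all participants correct.

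A reader might infer more than the documents support:

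- **That Group A is also scheduled below 15.** Group A's base rate ("In weeks 10-24, days for sample collection will reduce to once every 2-3 weeks on average", after about every other test day in weeks 4-9) looks low. But the plan adds randomly selected test days in Group A to match running averages in Group C, and prompts Group B at the same frequency. The base rate is not what those patients will be asked for.
- **That the average over all patients straddles the minimum.** The benefits section mentions phone service "so long as they provide study-requested samples, estimated average of 18-23 per patient". It names no period, so subtracting the six samples of weeks 1-3 to get an average for weeks 4-24 rests on an assumption.
- **That many patients will exceed 35.** The Research Strategy says that about 30%-50% of patients never achieve abstinence under reinforcement interventions. That figure comes from other studies, and it does not say how many such patients would keep submitting samples here. The documents give no frequency.

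The consent pages are not in the documents reviewed, so the form's actual wording could not be checked. The point rests on the protocol's statement of what the form will say.

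**Conclusion.** The stated range of 15 to 35 is wrong at both ends when read, as written, as a range for all participants. The schedule gives about 12 on average in weeks 4-24 for a Group C patient negative at every test, and allows up to 42 in any group. The figure of 12 follows from the plan's own phase rates and is confirmed by its totals of 18 samples and 231 draws. It is an average, not a minimum, and applies only to patients with no or very few lapses. The figure of 42 is the number of test days in weeks 4-24. It is a worst case under the rules as written, and the excess of 7 (20%) should not be read as typical.

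This is a minor correction to participant information. Nothing in it bears on the primary endpoint, the power calculation or the Aim 2 comparison of the two reinforcement conditions.

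**What to change.** In item b.ii, and in the consent form if it carries the same range, replace the phrase giving 15 to 35 samples in weeks 4-24 with wording such as:

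*The number of samples will vary: about 12 on average in the adaptive group if all samples are submitted and negative, and possibly more in any group, up to a maximum of 42 (both test days every week), depending on group, missed samples, test results and randomly added test days.*

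The mention of randomly added days matters, because Group A can receive them without missing a sample. Do not put an all-patient average or a Group A base figure into the form, since the documents do not establish either.

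Leave the Group C schedule as it is, so that the balance of about 231 draws in Group C against 229 in Group B is kept. The cost is one phrase in the protocol and one in the consent form, with no change to visits, samples, sample size or analysis.
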